### 5.6.3. Pulmonary Immune-related Adverse Events

Rule out non-inflammatory causes, if non-inflammatory cause is identified, treat accordingly and continue therapy per protocol. Evaluate with imaging and pulmonary consultation.

**Table 6: Pulmonary Immune-related Adverse Event Management Algorithm**

Pulmonary Immune-related Adverse Events		
Grade of Pneumonitis (NCI CTCAE v4.03)	Management	Follow-Up
Grade 1 Radiographic changes only.	
 
Consider delay of AGEN2034 therapy per protocol.
 
Monitor for symptoms every 2–3 days.
 
Consider pulmonary and infectious disease consults.
 
	
 
Re-image every <math>\geq 3</math> weeks.
 
If worsens: treat as Grade 2 or Grade 3–4.
 

Grade 2 Mild to moderate new symptoms	
 
Delay AGEN2034 therapy per protocol.
 
Pulmonary and infectious disease consults.
 
Monitor symptoms daily; consider hospitalization.
 
1 mg/kg/day methylprednisolone IV or oral equivalent.
 
Consider bronchoscopy, lung biopsy.
 
	
 
Re-image every 1–3 days.
 
If improves: when symptoms return to near baseline, taper corticosteroids over at least 1 month, then resume AGEN2034 therapy per protocol, and consider prophylactic antibiotics.
 
If not improving after 2 weeks or worsening: treat as Grade 3–4.
 

Grade 3–4 Severe new symptoms; new/worsening hypoxia; life-threatening.	
 
Discontinue AGEN2034 therapy per protocol.
 
Hospitalize.
 
Pulmonary and infectious disease consults.
 
2–4 mg/kg/day methylprednisolone IV or IV equivalent.
 
Add prophylactic antibiotics for opportunistic infections.
 
Consider bronchoscopy, lung biopsy.
 
	
 
If improves to baseline: taper corticosteroids over at least 6 weeks.
 
If not improving after 48 hours or worsening: add additional immunosuppression (e.g., infliximab, cyclophosphamide, IV immunoglobulin, mycophenolate mofetil).
 

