#### **4.4. Criteria for Subject Withdrawal**

##### **4.4.1. Withdrawal from Treatment**

The subject must be withdrawn in the event of any of the following:

- Occurrence of an event that would have been considered an exclusion criterion prior to enrollment, that is clinically relevant and affects the subject's safety, and if discontinuation is considered necessary by the investigator and/or Sponsor.
- Radiological disease progression, defined by RECIST 1.1 as defined in [Section 6.4.4.3](#), unless the subject is considered to derive clinical benefit from the treatment by the investigator, is clinically stable and there is agreement with the Sponsor ([Section 5.4.5](#)).

Clinical stability is defined by:

- Absence of new symptoms and signs indicating clinically significant disease progression
- No decline in ECOG performance status.
- Absence of rapid progression of disease or progressive tumor at critical anatomical sites (e.g., cord compression) requiring urgent alternative medical intervention.

- Note: For Phase 2, tumor assessments should be performed every 6 weeks ( $\pm$  3 days) from first treatment dose until discontinuation of treatment, regardless of reason for discontinuation. This includes patients who are being treated past disease progression. Clinical disease progression, in the absence of radiologic progression on the basis of RECIST 1.1, including 1 or more of the following:
  - signs and/or symptoms of consistent with clinically significant progression of disease, including worsening of laboratory values, appearance of new lesion/worsening of the lesion best seen clinically, etc.
  - decline in ECOG performance status
  - tumor progression at critical anatomical sites that requires urgent medical intervention (e.g., CNS metastasis with potential for cord progression)
  - initiation of chronic opiates, or initiation of chemotherapy or new antineoplastic therapy, palliative radiation therapy, or surgery
- Any Grade 2 drug-related uveitis or eye pain or blurred vision that does not respond to topical therapy and does not improve to Grade 1 severity within 2 weeks OR requires systemic treatment;
- Any Grade  $\geq$  2 drug-related pneumonitis or interstitial lung disease that does not resolve to dose delay and systemic corticosteroids (also see Pulmonary Immune Related Adverse Event Management Algorithm [[Section 5.6.3](#)]);
- Any Grade 2 or 3 drug-related toxicity that does not resolve in  $\leq$  6 weeks;

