- Any Grade 3 drug-related bronchospasm, hypersensitivity reaction, or infusion-related reaction, regardless of duration; with the exception of Grade 3 infusion-related reactions resolving within 6 hours and controlled with medical management;
- Any Grade 3 non-skin, drug-related AE lasting  $>$  7 days, with the following exceptions for uveitis, pneumonitis, bronchospasm, diarrhea, colitis, neurologic toxicity, hypersensitivity reactions, infusion reactions, endocrinopathies, and laboratory abnormalities:
  - Grade 3 drug-related uveitis, pneumonitis, bronchospasm, diarrhea, colitis, neurologic toxicity, hypersensitivity reaction, or infusion reaction of any duration requires discontinuation;
  - Grade 3 drug-related endocrinopathies adequately controlled with only physiologic hormone replacement do not require discontinuation;
  - Grade 3 drug-related laboratory abnormalities do not require treatment discontinuation except:
    - Grade 3 drug-related thrombocytopenia  $>$  7 days or associated with bleeding requires discontinuation;
    - Any drug-related liver function test (LFT) abnormality that meets the following criteria require discontinuation (also see hepatic immune-related AE management algorithm [[Table 7](#)]):

- ▶ AST or ALT  $> 8 \times$  ULN;
- ▶ Total bilirubin  $> 5 \times$  ULN;
- ▶ Concurrent AST or ALT  $> 3 \times$  ULN AND total bilirubin  $> 2 \times$  ULN;
- Any Grade 4 drug-related AE or laboratory abnormality, except for the following events, which do not require discontinuation:
  - Grade 4 neutropenia  $< 7$  days;
  - Grade 4 lymphopenia or leukopenia;
  - Isolated Grade 4 electrolyte imbalances/abnormalities that are not associated with clinical sequelae and are corrected with supplementation/appropriate management within 72 hours after their onset;
- Any AE, laboratory abnormality, or intercurrent illness which, in the judgment of the Investigator, presents a substantial clinical risk to the subject with continued treatment;
- Tumor flare phenomenon, defined as local pain, irritation, or rash localized at sites of known or suspected tumor does not require treatment discontinuation.
- Any requirement for  $\geq 10$  mg per day of prednisone (or equivalent) for  $> 6$  weeks;
- Any recurrence of a Grade 3 or 4 drug-related toxicity;
- Dose delay which results in no AGEN2034 dosing for more than 6 weeks.

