#### 5.4.4.2.2. *Criteria to Resume Treatment*

Subjects may resume treatment with AGEN2034 when drug-related AE(s) resolve(s) to Grade 1 or baseline value, with the following exceptions:

- Subjects may resume treatment in the presence of Grade 2 fatigue.
- Subjects who have not experienced a Grade 3 drug-related skin AE may resume treatment in the presence of Grade 2 skin toxicity.

- Subjects with baseline Grade 1 AST/ALT or total bilirubin who require dose delays for reasons other than a 2-Grade shift in AST/ALT or total bilirubin may resume treatment in the presence of Grade 2 AST/ALT or total bilirubin.
  - Subjects with combined Grade 2 AST/ALT AND total bilirubin values meeting discontinuation parameters ([Section 4.4.1](#)) should have treatment permanently discontinued.
- Drug-related pulmonary toxicity, diarrhea, or colitis must have resolved to baseline before treatment is resumed.
- Drug-related endocrinopathies adequately controlled with only physiologic hormone replacement may resume treatment.
- Subjects who received systemic corticosteroids for management of any drug-related toxicity must be off corticosteroids or have tapered down to an equivalent dose of prednisone  $\leq$  10 mg/day.

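### After Grade 2 pneumonitis, Table 6 and sections 4.4.1, 5.4.4.2.2 and 6.4.1.11 do not give one restart point or one consequence once six weeks pass without dosing

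*Protocol*

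**What the plan says.** Four places in the protocol bear on a subject whose Grade 2 pneumonitis comes under control.

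- **Table 6 (section 5.6.3), Grade 2 follow-up.** On improvement, once symptoms are near baseline, the instruction is: "taper corticosteroids over at least 1 month, then resume AGEN2034 therapy per protocol". The same cell sets a cut-off for failure to improve: "If not improving after 2 weeks or worsening: treat as Grade 3–4".
- **Section 5.4.4.2.2.** A subject who received systemic steroids for a drug-related toxicity "must be off corticosteroids or have tapered down to an equivalent dose of prednisone" of no more than 10 mg/day, so the taper need not be finished. It also states: "Drug-related pulmonary toxicity, diarrhea, or colitis must have resolved to baseline before treatment is resumed".
- **Section 4.4.1.** The list opens with "The subject must be withdrawn in the event of any of the following" and includes "Dose delay which results in no AGEN2034 dosing for more than 6 weeks". No exemption is made for a taper that the protocol itself requires. A separate item withdraws Grade 2 or higher "drug-related pneumonitis or interstitial lung disease that does not resolve to dose delay and systemic corticosteroids" and points to section 5.6.3. Subjects who do resolve are therefore meant to have a route back to treatment.
- **Section 6.4.1.11.** If toxicity puts more than six weeks between doses, the investigator and Sponsor are to confer and record a joint decision on the subject. Withdrawal is not automatic.

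Phase 2 dosing is every 2 weeks (section 5.4.1.1).

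**The concern.** Table 6 puts resumption after a taper of at least one month. Section 5.4.4.2.2 allows it earlier. Section 4.4.1 may already have required withdrawal by the time the Table 6 taper ends, and section 6.4.1.11 would send that same subject to a case-by-case decision. The order in Table 6 does not look like loose drafting. Tables 4, 5, 7, 8 and 9 list taper and resumption side by side, joined by a conjunction or semicolon or set as separate bullets. Only the pulmonary table makes one follow the other.

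At stake is whether the same subject is re-treated, withdrawn or referred for a decision. With approximately 60 Phase 2 centers planned (section 11.2), sites could act differently on identical facts. The effect reaches the planned safety output: SAP section 7.6.2 reports, for the pneumonitis cluster, the percentages leading to dose hold and to drug discontinuation.

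**Working it through.** The plan states no figure on this point, so there is none to reproduce. The check is a timeline.

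**Inputs from the protocol**
- Limit without dosing: 6 weeks = 42 days (4.4.1).
- Taper: at least 1 month, taken as 28, 30 or 31 days (Table 6). This is a minimum.
- Dosing interval: 14 days (5.4.1.1).

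**Inputs assumed, because the documents do not give them**
- *d*, days from last dose to onset: uniform over 0–14.
- *t*, days from onset to near-baseline symptoms: uniform over 1–7, 0–14, 3–14 or 7–14. The upper value of 14 is borrowed from the non-improvement cut-off. It is not a protocol limit on time to near baseline.

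**Formula.** Interval since last dose = *d* + *t* + taper. The 4.4.1 limit is passed when this exceeds 42.

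**Room left.** 42 − 28 = 14 days; 42 − 30 = 12; 42 − 31 = 11. So *d* + *t* must fit within 11–14 days.

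**Two cases with a 30-day taper**
- *d* = 3, *t* = 5: 3 + 5 + 30 = 38 days. The subject can follow Table 6 and stay within 4.4.1.
- *d* = 10, *t* = 7: 10 + 7 + 30 = 47 days. Table 6 says resume, 4.4.1 says withdraw, and 6.4.1.11 says confer.

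**Range.** The shortest interval is 28–31 days. With *d* and *t* both at 14, the longest is 56–59 days.

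**Share passing 42 days, counted from the last dose, every-2-week dosing**

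| Assumed *t* (days) | Taper 28 | Taper 30 | Taper 31 |
|---|---|---|---|
| 1–7 | 29% | 43% | 50% |
| 0–14 | 50% | 63% | 69% |
| 3–14 | 61% | 74% | 79% |
| 7–14 | 75% | 87% | 92% |

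These come from 2,000,000 simulated draws per setting. Two rows can be checked by hand, with *s* as the room left:
- *t* over 0–14: share = 1 − *s*²/(2 × 14²). For *s* = 14, 12, 11 this is 1 − 196/392 = 50%, 1 − 144/392 = 63%, 1 − 121/392 = 69%.
- *t* over 1–7 (mean 4): share = (14 − *s* + 4)/14, giving 4/14 = 29%, 6/14 = 43%, 7/14 = 50%.

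**Sensitivity to the assumptions**
- Onset always within 3 days of dosing: 0–64%.
- Event first found at the next dosing visit (*d* = 14): 14 + *t* + 28 already exceeds 42 for any *t* above 0, so 100%.
- Six weeks counted from the missed dose: the limit becomes 42 + 14 = 56 days since the last dose, and the share falls to 0–5%.
- Every-3-week dosing (Phase 1 Part A2), same *t* ranges, *d* uniform over 0–21: 52–95%.

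**Difference between the two restart points.** The documents give no taper shape. Purely as an illustration, a linear taper over *T* days from *S* mg/day prednisone equivalent reaches 10 mg/day on day *T*(1 − 10/*S*). With *S* from 50 to 100 and *T* from 28 to 31, that is 2.8–6.2 days before the taper ends. With *t* over 0–14, the share past 42 days is then 18–49%, against 50–69% for restart at the end of the taper.

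**The case against.** The best defence is that the rules can be followed together. Section 5.4.4.2.2 sets general conditions under which subjects may resume, and a subject who has finished the Table 6 taper meets its off-steroids condition. A stricter sequence for one organ, on top of a general minimum, is not in itself a contradiction. Table 6 also says to resume per protocol, section 5.5.1.1 sends readers to 5.4.4.2.2 on continuing treatment, and section 5.6 describes the algorithms as an aid to investigators. This softens the Table 6 versus 5.4.4.2.2 difference but does not remove it. If 5.4.4.2.2 governs, the sequence in Table 6 is misleading. If Table 6 governs, it adds a month-long step that 4.4.1 does not allow for. Neither reading settles 4.4.1 against 6.4.1.11.

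A reader might also infer three things that the documents do not support.

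- *That most subjects on the resume path would have to be withdrawn.* No onset or improvement times are given. The share is below half in some of the settings above, runs from 0% to 100% across all of them, and depends on where the clock starts. Section 6.4.1.11 also provides something other than withdrawal.
- *That near baseline in Table 6 conflicts with baseline in 5.4.4.2.2.* The first triggers the taper and the second is a condition for restart. They apply at different steps.
- *That Table 6 allows two weeks to improve.* It sets a point at which lack of improvement is escalated. Time to near baseline is not capped.

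It is also fair to say that the documents give no expected number of Grade 2 pneumonitis cases, and that no effect on the primary ORR analysis has been shown.

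**Conclusion.** The inconsistency is real and can be seen in the text without any simulation. Table 6 and 5.4.4.2.2 place restart at different points. Table 6's taper uses 28–31 of the 42 days in 4.4.1, with no exemption. Sections 4.4.1 and 6.4.1.11 prescribe different consequences for the same delay.

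The size is conditional. If the clock starts at the last dose, a substantial share of subjects following Table 6 could meet both the resume and the withdrawal instruction: about 29–92% for every-2-week dosing under the main assumptions. If it starts at the missed dose, the overlap is 0–5%. The wording of 4.4.1 and of 6.4.1.11, which refers to the time between doses, favors the last dose, but neither section fixes the starting day. The percentages rest on assumed uniform onset and improvement times and should be read as a range. The consequence falls on consistency of management across sites and on the SAP's pneumonitis dose-hold and discontinuation percentages.

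**What to change.** Reconcile Table 6, 4.4.1, 5.4.4.2.2 and 6.4.1.11 so that together they state:

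1. one restart condition after Grade 2 pneumonitis, covering both symptom level and steroid status;
2. one starting point for the six-week clock;
3. one consequence when six weeks is passed while a required taper is running, either withdrawal or a documented investigator–Sponsor decision.

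The clinical team must choose the rule; none is proposed here. The cost is a short protocol clarification in those four places. Sample size and the planned analyses are unchanged.

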### 5.6.4. Hepatic Immune-related Adverse Events

Rule out non-inflammatory causes, if non-inflammatory cause is identified, treat accordingly and continue therapy per protocol. Consider imaging for obstruction.

**Table 7: Hepatic Immune-related Adverse Event Management Algorithm**

Hepatic Immune-related Adverse Events		
Grade of Liver Test Elevation (NCI CTCAE v4.03)	Management	Follow-Up
Grade 1 AST or ALT >ULN to 3 x ULN and/or total bilirubin >ULN to 1.5 x ULN.	
 
Continue AGEN2034 therapy per protocol.
 
	
 
Continue liver function tests (LFT) monitoring per protocol.
 
If worsens: treat as Grade 2 or Grade 3–4.
 

Grade 2 AST or ALT >3 to ≤5 x ULN and/or total bilirubin >1.5 to ≤3 x ULN.	
 
Delay AGEN2034 therapy per protocol.
 
Increase frequency of monitoring to every 3 days.
 
If subject has concurrent AST or ALT > 3 x ULN AND total bilirubin > 2 x ULN, Discontinue AGEN2034 therapy per protocol.
 
	
 
If returns to baseline: resume routine monitoring; resume AGEN2034 therapy per protocol.
 
If elevations persist >5 to 7 days or worsen: 0.5–1 mg/kg/day methylprednisolone IV or oral equivalent. When LFT returns to Grade 1 or baseline, taper corticosteroids over at least 1 month, consider prophylactic antibiotics for opportunistic infections, and resume AGEN2034 therapy per protocol.
 

Grade 3–4 AST or ALT >5 x ULN and/or total bilirubin >3 x ULN.	
 
Discontinue AGEN2034 therapy per protocol.
 
Increase frequency of monitoring to every 1–2 days.
 
1–2 mg/kg/day methylprednisolone IV or oral equivalent*.
 
Add prophylactic antibiotics for opportunistic infections.
 
Consult gastroenterology.
 
Consider obtaining MRI/CT scan of liver and liver biopsy if clinically warranted.
 
	
 
If returns to Grade 2: taper corticosteroids over at least 1 month.
 
If does not improve in > 3 to 5 days, worsens or rebounds: add mycophenolate mofetil 1 g twice daily. If no response within an additional 3–5 days, consider other immunosuppressants per local guidelines.
 

\*The recommended starting dose for Grade 4 hepatitis is 2 mg/kg/day methylprednisolone IV.

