5. Have a life expectancy of at least 3 months and an Eastern Cooperative Oncology Group (ECOG) performance status of 0 or 1.
6. Have adequate organ function as indicated by the following laboratory values:
  - a. Adequate hematological function defined by absolute neutrophil count (ANC)  $\geq 1.5 \times 10^9/L$ , platelet count  $\geq 100 \times 10^9/L$ , and stable hemoglobin  $\geq 8 \text{ g/dL}$  (without transfusions within 1 week before first dose).
  - b. Adequate hepatic function based by a total bilirubin level  $\leq 1.5 \times$  the institutional upper limit of normal (IULN), aspartate aminotransferase (AST) level  $\leq 2.5 \times$  IULN, alanine aminotransferase (ALT) level  $\leq 2.5 \times$  IULN, and alkaline phosphatase  $\leq 2.5 \times$  IULN.
  - c. Adequate renal function defined as creatinine  $\leq 1.5 \times$  IULN **OR** calculated creatinine clearance  $\geq 50 \text{ mL/min}$  for subjects with creatinine levels  $> 1.5 \times$  IULN (if no local guideline is available, creatinine clearance should be calculated using the Cockcroft-Gault Method).
  - d. Adequate coagulation defined by international normalized ratio (INR) or prothrombin time  $\leq 1.5 \times$  IULN (unless the subject is receiving anticoagulant therapy); and activated partial thromboplastin time (aPTT)  $\leq 1.5 \times$  IULN (unless the subject is receiving anticoagulant therapy)
7. Other than the cancer for which the subject is enrolled, have no history of prior malignancy, with the exception of basal cell carcinoma of the skin, superficial bladder cancer, squamous-cell carcinoma of the skin, or has undergone potentially curative therapy with no evidence of that disease recurrence for 5 years since initiation of that therapy.
8. In Phase 2, subjects must provide a sufficient and adequate formalin-fixed paraffin embedded (FFPE) tumor tissue sample preferably from the most recent biopsy of a tumor lesion, collected either at the time of or after the diagnosis of advanced or metastatic disease has been made AND from a site not previously irradiated. If no tumor tissue is available, a fresh biopsy will be required. (See [Section 6.4.2.1](#) for details.)

**Note:** Tissue from needle or excisional biopsy or from resection is required.

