### 5.4.4.2. Treatment Delay

#### 5.4.4.2.1. *Criteria for Treatment Delay*

AGEN2034 administration should be delayed for the following:

- Any Grade  $\geq 2$  non-skin, drug-related AE with the following exceptions:
  - Do not delay treatment for Grade  $\geq 2$  Fatigue and laboratory abnormalities except for:
    - Delay dosing for Grade  $\geq 2$  serum creatinine (more than 1.5x baseline) toxicity
    - If a subject has a baseline AST, ALT, or total bilirubin that is within normal limits, delay dosing for drug-related Grade  $\geq 2$  toxicity;
- Any Grade  $\geq 3$  skin drug-related AE or suspected Stevens-Johnson syndrome (SJS) or toxic epidermal necrolysis (TEN)
- Any Grade  $\geq 3$  drug-related laboratory abnormality with the following exceptions for lymphopenia, AST, ALT, or total bilirubin:
  - Grade 3 lymphopenia does not require a dose delay.
  - If a subject has a baseline AST, ALT, or total bilirubin that is within normal limits, delay dosing for drug-related Grade  $\geq 2$  toxicity.
  - If a subject has baseline AST, ALT, or total bilirubin within the Grade 1 toxicity range, delay dosing for drug-related Grade  $\geq 3$  toxicity.
- Any AE, laboratory abnormality, or inter-current illness which, in the judgment of the investigator, warrants delaying the dose of study drug.

Subjects receiving AGEN2034 who have drug-related toxicities that meet the criteria for dose delay should have treatment delayed until retreatment criteria are met.

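### For subjects enrolled with Grade 1 liver tests, Table 7 and Section 5.4.4.2 of the protocol give conflicting instructions for a Grade 2 elevation, most clearly on corticosteroids

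*Protocol*

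**What the plan says.** Protocol 5.6.4, Table 7, defines Grade 1 as "AST or ALT >ULN to 3 x ULN and/or total bilirubin >ULN to 1.5 x ULN" and Grade 2 as "AST or ALT >3 to ≤5 x ULN and/or total bilirubin >1.5 to ≤3 x ULN". The Grade 2 row makes no reference to the baseline value. Its instructions are:

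- "Delay AGEN2034 therapy per protocol", with more frequent monitoring.
- If values return to baseline, resume drug, again per protocol.
- If elevations last more than "5 to 7 days or worsen", give "0.5–1 mg/kg/day methylprednisolone IV or oral equivalent. When LFT returns to Grade 1 or baseline, taper corticosteroids over at least 1 month", then resume per protocol.

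The text before the table requires non-inflammatory causes to be ruled out first.

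Section 5.4.4.2.1 does distinguish by baseline. A normal baseline means delay at drug-related Grade 2 or above. Otherwise the rule is "If a subject has baseline AST, ALT, or total bilirubin within the Grade 1 toxicity range, delay dosing for drug-related Grade" 3 or above. Section 5.4.4.2.2 adds that subjects with a Grade 1 baseline, if delayed for a reason other than a 2-Grade shift in these tests, "may resume treatment in the presence of Grade 2 AST/ALT or total bilirubin". It also requires anyone given systemic corticosteroids for a drug-related toxicity to be off them, or at 10 mg/day prednisone equivalent or less, before resuming.

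Section 4.2, criterion 6b ("Adequate hepatic function based by a total bilirubin level" and what follows), admits total bilirubin up to 1.5 x IULN and AST or ALT up to 2.5 x IULN.

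**The concern.** Subjects with a Grade 1 baseline are eligible, and Section 5.4.4.2 has a rule written for them. Table 7, the page a site is likely to open when liver tests rise, has no such rule. If the elevation persists, one text requires no interruption, while the other leads to interruption and systemic immunosuppression.

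The choice has consequences in the trial's own rules. Once steroids start, the 10 mg/day condition in 5.4.4.2.2 applies. Two withdrawal criteria in 4.4.1 also come into play: 10 mg/day or more of prednisone for over 6 weeks, and no dosing for over 6 weeks. Without a hold or steroids, neither clock starts.

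Reported results are touched as well. Protocol 8.3.4 counts dose delays. SAP 7.6.2 reports dose holds and systemic corticosteroid use for immune-mediated clusters, so an event coded to one of its hepatitis terms would contribute. These counts could differ between sites because of the page followed rather than the drug.

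**Working it through.** No figure in the plan needs reproducing. The check is whether the conflict applies to eligible subjects, and then what each text tells a site to do.

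**Step 1: eligible baselines against the Table 7 bands (multiples of ULN)**

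| Test | Eligible and above ULN | Grade 1 band | Grade 2 band |
|---|---|---|---|
| AST or ALT | >1.0 to 2.5 | >1.0 to 3.0 | >3.0 to 5.0 |
| Total bilirubin | >1.0 to 1.5 | >1.0 to 1.5 | >1.5 to 3.0 |

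Every eligible value above ULN is a Grade 1 baseline.

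**Step 2: distance to Grade 2**

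- AST/ALT from 2.5: 3.0 / 2.5 = 1.20, a 20% rise to the boundary. The band ends at 5.0 / 2.5 = 2.0-fold.
- Bilirubin from 1.5: 1.5 / 1.5 = 1.0, so any rise enters Grade 2. The band ends at 3.0 / 1.5 = 2.0-fold.

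**Step 3: one subject under both texts**

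Take baseline ALT 2.4 x ULN, then a drug-related ALT of 3.3 x ULN (3.3 / 2.4 = 1.375, a 38% rise) for more than 7 days, with normal bilirubin and no non-inflammatory cause found.

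| Step | Section 5.4.4.2 | Table 7, read literally |
|---|---|---|
| Delay | Not required below Grade 3 | Delay, per protocol |
| Steroids | Silent | Methylprednisolone, because the elevation has persisted |
| Restart, if held | Generally Grade 1 or baseline; Grade 2 allowed if the hold was not for a 2-Grade shift | Baseline without steroids; Grade 1 or baseline, with taper, after steroids |

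Grade 1 to Grade 2 is a shift of one grade (2 − 1 = 1), so the Grade 2 allowance in 5.4.4.2.2 is open to this subject. The two parts of 5.4.4.2 agree with each other: from a Grade 1 baseline, a 2-Grade shift is Grade 3, which is the delay threshold.

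**Step 4: do both texts reach the same subject?**

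Yes. Section 7.1.8 assumes an event to be immune-related when no other cause is found, so a drug-related elevation without another explanation comes under Table 7 as well as 5.4.4.2.

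**Step 5: where there is no conflict**

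- Normal baseline: both texts delay at Grade 2.
- AST or ALT above 3 x ULN together with bilirubin above 2 x ULN: discontinued in both 4.4.1 and Table 7.
- A Grade 2 clinical event such as hepatitis, as opposed to a laboratory abnormality, falls under the general delay rule for non-skin events in 5.4.4.2.1.

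**The case against.** The best defence is that the sections divide the work: 5.4.4.2 governs dosing, and Table 7 governs work-up and treatment. In the Grade 2 row both the delay and the resume statements carry the per-protocol qualifier. Section 5.5.1.1 sends readers to 5.4.4.2.2 for continuing treatment and to 5.6 for the algorithms, and it says steroids should be considered according to type and severity. Section 5.6 describes the algorithms as an aid to investigators. Much of this stands, and it softens the conflict over delay and restart.

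It does not settle the steroid step, which has neither the qualifier nor a baseline exception. If the delay is deferred to 5.4.4.2.1, the subject in Step 3 need not be held, yet after a week would still be directed to methylprednisolone. Nor does any statement set precedence. Section 4.4.1 sends the reader to Table 7 for liver tests, and Table 7 sends the reader back to the protocol.

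It is also fair to say that 5.4.4.2 does not keep every such subject on drug. The investigator may delay for any laboratory abnormality that warrants it, and 4.4.1 withdraws for Grade 2 or 3 drug-related toxicity unresolved within 6 weeks. These limits narrow the conflict but do not remove it.

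A reader might infer from Table 7 that steroids follow any Grade 2 elevation. The text does not support that: persistence or worsening is required, after non-inflammatory causes have been ruled out.

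**Conclusion.** Wrong as written: an internal contradiction. It affects an eligible subject with Grade 1 baseline AST, ALT or bilirubin who has a drug-related, suspected immune-related Grade 2 elevation, with non-inflammatory causes ruled out and the concurrent discontinuation criterion not met. It is clearest once the elevation persists or worsens, because the steroid step then applies without qualification.

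The number of affected subjects cannot be sized. The documents do not say how many subjects have a Grade 1 baseline, how many of those reach Grade 2 on drug, or how often the elevation persists. Two stronger conclusions might be inferred, and neither is supported:

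- **A count.** If 10% to 25% of about 150 subjects had a Grade 1 baseline (an assumption), that would be 15 to 38 subjects (0.10 x 150 = 15; 0.25 x 150 = 37.5). This counts subjects at risk of meeting the conflict, not those who do.
- **Missed doses.** A taper of at least 1 month on a 2-week schedule suggests at least two lost doses. But 5.4.4.2.2 permits dosing once the prednisone equivalent is 10 mg/day or less, which may come before the taper ends.

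No effect on the confirmed response rate is shown. The reason to correct this is that a safety instruction deciding drug interruption and immunosuppression should not depend on which page is read.

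**What to change.** Reconcile the Grade 2 row of Table 7 (delay, steroid trigger and restart point) with Sections 5.4.4.2.1 and 5.4.4.2.2, so that both places give the same rule by baseline grade. Alternatively, add one sentence saying which section governs each step, the steroid step included. The sponsor's clinical team decides which rule stands; this review takes no view.

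The cost is a wording change to one table row and a cross-reference at the next amendment. No additional data are needed.
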